Investigational product, dosage and mode of administration:

INT230-6 administered intratumorally, a fixed combination of cisplatin, vinblastine and SHAO

Duration of treatment:

In A1 and B1 cohorts, subjects received injections monthly for up to 5 doses of INT230-6 (4 months). In E cohorts, injections are given every 2 weeks for up to 5 doses. Cohorts EC3, DEC2, FEC and potentially GEC will utilize the once every 2 weeks dosing for 5 doses followed by maintenance dosing once every 9 weeks +/- 10 days until CR, PD or 2 years, whichever is first. Given the short half-life of the components of INT230-6, safety follow up post the last dose of treatment is 28 days for monotherapy cohorts. Subjects are followed regularly until progression and/or start of subsequent anti-cancer therapy. Afterwards subjects will transition to a less frequent survival follow up. The total expected duration of the study is 5 years.

Reference therapy, dosage and mode of administration:

NA

Criteria for evaluation:

Efficacy:

Since this is a locally administered product, it allows for multiple efficacy analyses. The primary efficacy measure will be disease control rate (CR+PR+SD) as assessed by iRECIST. Since immune system activation is expected from preclinical studies, the trial will collect samples from the peripheral blood and from tumors to look at markers of activation. Furthermore, observing tumor shrinkage in non-injected bystander tumors would also indicate potential immune activation. In order to take the whole picture into account, the exploratory endpoints will look at overall tumor response, time to progression and overall survival.

Safety:

Assessment of safety will be determined by ongoing review of clinical laboratory tests (blood and urine sampling for clinical laboratory parameters), pregnancy testing, Eastern Cooperative Oncology Group (ECOG) performance status, physical examination including vital sign measurements, any needed or completed electrocardiogram (ECG), and adverse events.

Pharmacokinetic:

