5 CBC with Differential, Chemistry and Urinalysis as outlined in Section 12.1.2. Grade 3 laboratory abnormality should be assessed for potential risk to continued dosing. In the event of uncertainty, the Sponsor medical monitor should be contacted. ≥ Grade 3 laboratory abnormality should be assessed for potential risk to continued dosing.

6 Serum or urine pregnancy testing must be performed for woman of childbearing potential and found to be negative before dosing.

7 ECOG performance status to be assessed before each injection.

8 Measurements used to guide placement of the needle for injection.

9 The same technique (CT/MRI or PET/CT) used at screening should be used throughout the study.

10 Investigators will assess tumor response using CT/MRI or PET/CT measurements. Assessments should occur 12 weeks +/- 10 days from the first dose (Cycle 1, D0) and then every 9 weeks +/- 10 days for every image thereafter.

11 Tumor imaging only needs to be collected if it has not occurred within the last 29 days.

12 Serum based disease markers if appropriate will be collected at the same timepoints as tumor imaging. Other imaging to be collected as clinically indicated (i.e., brain scans, etc.).

13 Subjects must consent to fresh repeat biopsies of tumors taken prior to dosing on days 0 and 28 (day 0 in cycle 2) during the course of the study at injection sites are mandatory unless cleared by the Sponsor medical monitor. Additionally, 1 biopsy of an untreated bystander tumor that is readily accessible without the need for general anesthesia should be taken by the attending physician if possible; however, if risk too high such bystander biopsy should not be taken. **The post-dose biopsy sample must be taken from the same lesion(s) that were collected at pre-dose (C1D0). If there is an issue that precludes the ability to biopsy the same pre-dose lesion at the later timepoint (C2D0), please inform the Medical Monitor and attempt to biopsy from the pre-dose lesions during a subsequent visit.**

14 Baseline ECG to be done and repeated only if medically indicated throughout the study.

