		SECONDARY	
1) Characterize the overall safety of the combination
 
2) Assess the preliminary efficacy of INT230-6 with Ipilimumab by measuring the injected and bystander tumor response
 
3) Characterize the pharmacokinetic profile of multiple doses of the three INT230-6 components cisplatin (CIS), vinblastine sulfate (VBL) and the cell penetration enhancer (SHAO) after single and then multiple IT tumor site injections
	
1) Grade 3 or higher adverse events attributed to the combination and not the underlying disease
 
Incidence and severity of treatment-emergent adverse events (TEAEs)
 
Clinical laboratory results (hematology, chemistry, urinalysis)
 
ECOG performance status
 
Physical examination, including vital sign measurements
 
ECG results
 
2) Injected and Bystander Response Rates
 
3) C_{max}, C_{min}, T_{max}, AUC_{TAU}, Accumulation index

		EXPLORATORY	
1) Characterize tumor response in injected and non-injected sites
 
2) Evaluate various tumor and anti-tumor immune response biomarkers that may correlate with tumor response
 
3) Evaluate overall response by criteria based on RECIST or iRECIST
 
4) Characterize the pharmacodynamics (PD) profile of the INT230-6 formulation in subject blood and treated and untreated tumors
 
5) To assess the progression free (PFS) and overall survival (OS) in subjects receiving INT230-6.
 
6) Explore the activity of the combination of INT230-6 with Ipilimumab compared to INT230-6 alone in patients with the same tumor types such as sarcoma.
	
1) Injected and Bystander tumor response rates
 
2) Biomarker results
 
3) Response adjudicated as complete (CR), partial (PR), stable disease (SD), progressive disease (PD) or Not evaluable (NE); Best overall response and duration or response
 
4) PD profile results
 
5) PFS and OS as defined in Section 9.2 of this document
 
6) Subgroup analysis of efficacy endpoints

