 - The baseline value for a given parameter is the last non-missing value prior to the first dose. A value is considered to be post-baseline if it is obtained after the first study drug administration.

- Change from baseline is calculated as (post-baseline result – baseline result). Percent change from baseline is calculated as (change from baseline/baseline results * 100). If either the baseline or post-baseline result is missing, the change from baseline and/or percent change from baseline is set to missing as well.
- Data from study centers will be pooled for all analyses
- Study Day is defined as calendar date – date of first treatment + 1 if the calendar date is on or after the date of first treatment, and calendar date – date of first treatment if the calendar date is before the date of first treatment
- Measurements from unscheduled visits will be included in listings, but not summary tables
- Missing data conventions for individual endpoints are described in detail below for the endpoints
- Listings will be provided of all data collected in the electronic Case Report Form (eCRF)
- Wherever possible, data will be decimal aligned
- For continuous variables, use the following conventions for significant digits: mean (xx.x), median (xx.x), standard deviation (xx.xx), minimum (xx.x) and maximum (xx.x). If data results are less than 1, format decimal points to one more place than the measured value for all summary variables except format to two more places for standard deviations
- Version 25.1 of MedDRA will be used for this study.
- WHODRUG Enhanced Sep-2022 B3 will be used for this study.

The accompanying table, listing, figures (TLF) document to this SAP provides the expected layout and titles of the tables, figures, and listings. Any changes to format, layout, titles, numbering, or any other minor deviation will not necessitate a revision to the SAP nor will it be considered a deviation from planned analyses. Only true differences in the analysis methods or data handling will necessitate such documentation. Please refer to the SAP appendix for additional programming notes.

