9.1. Additional Efficacy Analysis

Additional efficacy parameters include the duration of response (DOR), the injected tumor response (ITR), the bystander tumor response (BTR), progression free survival (PFS), and overall survival (OS). These endpoints will be summarized by treatment (see section 7 for definition of each treatment) and subgroup. Other than 1 listing reporting bystander tumors' diameter that declined over time that declined (noted below), the bystander tumor response rate (BTR) analysis will be conducted separately from the SAP from collected radiographic data.

DOR is defined as the time from first tumor assessment of CR, PR, or SD to the time of progressive disease or death due to any cause. For responders with no death or progression, DOR will be censored on the last non-PD tumor assessment or follow-up call.

The median DOR as obtained from Kaplan-Meier methods will be presented by treatment and subgroup and will include the median, 25th percentile, 75th percentile, and a 2-sided point-wise 95% confidence interval.

ITR will be based on the target tumors at the baseline visit; tumors that become target during the study will also be included in the ITR calculation at the time they are treated. The ITR is defined as the ratio of CR + PR in injected tumors / total number of injected tumors. Thus, bystander or non-target lesions dosed at later dates are not included in calculations for ITR.

The ITR will be calculated based on the maximum likelihood estimator and summarized in tables. The estimate of ITR will be accompanied by 2-sided 95% exact binomial confidence intervals as determined by the Clopper-Pearson method and assessed at each study-specified timepoint where an assessment is performed.

The BTR will follow the same definition as the ITR for bystander tumors. Note that bystander tumors that are injected on study will be included in the ITR calculation.

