Individual tumor assessments for target and bystander, non-target, and new lesions will be listed, with location, method of assessment, longest diameter, shortest diameter, depth, volume, and percent change from baseline included for each target and bystander tumor, as well as Total Tumor Burden at Baseline, Cumulative Dose, Percent TTB dosed, and dose category (< 40% versus \geq 40%) per subject. Another listing will be produced for the Abscopal effect of bystander tumors, defined as any bystander tumor with any decrease in tumor size at any point during the study, but before being injected with study drug.

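### SAP 9.1 labels any decrease in a bystander tumor an abscopal effect, so reading error alone can earn the label, while the thresholded bystander rate (a FEC secondary endpoint) is analysed outside the SAP

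*SAP*

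**What the plan says.** SAP Section 9.1 states: "Another listing will be produced for the Abscopal effect of bystander tumors", which is "defined as any bystander tumor with any decrease in tumor size at any point during the study, but before being injected with study drug". An earlier paragraph of the same section describes apparently the same output as "1 listing reporting bystander tumors' diameter that declined over time". The definition does not say whether a decrease is judged against baseline, the previous scan or the smallest earlier value. SAP Section 7.1 has a general convention ("The baseline value for a given parameter is the last non-missing value prior to the first dose"), but the listing does not invoke it.

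SAP Section 9.1 first includes the bystander tumor response rate (BTR) among the endpoints to be summarized by treatment. It then says that "the bystander tumor response rate (BTR) analysis will be conducted separately from the SAP from collected radiographic data". In SAP Table 2 (Section 3.2) the FEC secondary endpoints include "Injected and Bystander Response Rates". The protocol synopsis says BTR will be tabulated. SAP Section 13 gives the changes from the protocol as none.

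The protocol synopsis says why bystander shrinkage matters: "observing tumor shrinkage in non-injected bystander tumors would also indicate potential immune activation".

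**The concern.** Abscopal effect is a causal label: it says that treating one tumor acted on another. The rule that awards it takes the most favourable of all scans and accepts any decrease, including a 1 mm difference between two readings of the same lesion. The study is open-label and non-randomized, so no untreated group shows how many tumors would qualify by chance.

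With BTR moved out, the only output in the SAP devoted to bystander tumors alone is one selected on shrinkage. A product with no distant effect would still fill it, and the study report could present those tumors under a heading that implies immune activation. The FEC secondary endpoint that uses a response threshold and a denominator would have no analysis in the SAP to set beside it.

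**Working it through.** The documents give no error rate for this listing and no measurement-error SD, so there is no stated figure to reproduce. The check asks how often a tumor with no true decrease meets the rule.

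**Inputs from the documents**
- Scans (footnote 10 to the schedule tables, Protocol 12.1.3): "Assessments should occur 12 weeks +/- 10 days from the first dose (Cycle 1, D0) and then every 9 weeks +/- 10 days". One to four post-baseline scans fall at weeks 12, 21, 30 and 39.
- Resolution: Protocol Appendix 1 (18.1.5) records lesions in millimetres, and the SAP Appendix example uses centimetres to one decimal.

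**Assumptions:** errors independent between scans; SD 0.5 to 3 mm; a 20 mm tumor; whole-millimetre readings unless stated.

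**Step 1. Unchanged tumor, continuous error.** The baseline and k follow-up readings are equally likely to be the smallest, so

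P(at least one follow-up below baseline) = k/(k+1).

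For k = 1, 2, 3, 4 this is 50%, 66.7%, 75% and 80%; for k = 8 it is 88.9%.

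**Step 2. Unchanged tumor, whole-millimetre diameters.** Ties do not count as decreases, so the rate falls and now depends on the SD (simulation):

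| Error SD | k = 1 | k = 2 | k = 3 | k = 4 |
|---|---|---|---|---|
| 0.5 mm | 24% | 35% | 43% | 50% |
| 1 mm | 36% | 52% | 60% | 66% |
| 2 mm | 43% | 59% | 68% | 74% |
| 3 mm | 45% | 62% | 70% | 76% |

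**Step 3. Other readings of the rule.** If tumor size means volume from three rounded dimensions, the range for k = 1 to 4 is 39% to 70% at SD 0.5 mm and 49% to 79% at SD 2 mm. If a decrease is judged against the previous scan, with continuous error, P = 1 − 1/(k+1)!, which is 50%, 83%, 96% and 99%.

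**Step 4. A tumor that truly grows.** At 5% growth per scan and 8% error (log scale, continuous), the label is given in about 33%, 41%, 43% and 43% for k = 1 to 4. With 1 mm error and whole-millimetre readings it is 15% to 17%.

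**Step 5. What a threshold does.** For unchanged tumors and k = 1 to 4 at 8% error per dimension (continuous), without confirmation:

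| Rule | Labelled |
|---|---|
| Diameter down at least 30% | 0.1% to 0.3% |
| Volume down at least 30%, three dimensions | 3% to 10% |
| Volume down at least 30%, longest diameter cubed | 15% to 35% |

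The volume rules are weaker because a 30% fall in volume is only 1 − 0.7^(1/3) = 11% in diameter. SAP Appendix 1 item 3 defines partial response by volume, and item 4 applies that method to bystander tumors.

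Confirmation matters most for small tumors. For an unchanged 10 mm tumor at SD 2 mm, a 30% diameter rule labels 12% (k = 1) to 34% (k = 4). Requiring two consecutive scans lowers this to 3% (k = 2) and 7% (k = 4). For a 20 mm tumor at the same SD, the unconfirmed rates are about 1% to 3%, and the confirmed rate at k = 4 is about 0.1%.

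**The case against.** The output is a single descriptive listing, with no rate, interval, test or decision rule attached. The sentence just before it in SAP Section 9.1 lists every target and bystander tumor individually with its percent change, so a reader can count a denominator. The protocol says only that shrinkage would indicate potential immune activation, alongside blood and tumor markers. BTR has not been dropped: the SAP still defines it and sends the analysis elsewhere. All of this stands, and it limits the consequence.

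A reader might infer that noise labels 50% to 80% of bystander tumors whatever the size of the error. The documents do not support that. The range is k/(k+1) for one to four scans, without ties and for unchanged tumors only. Readings in millimetres produce ties, and growing tumors are labelled less often. A reader might also infer that the denominator cannot be recovered; the individual listing shows that it can.

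Nor can the remedy simply import the SAP's own rules. The volume criterion in Appendix 1 item 3 leaves many false labels (step 5). The denominator in Appendix 1 item 4 varies by visit, whereas Protocol 12.2.2 counts confirmed responses over tumors identified at baseline. A 5 mm minimum shrinkage has no basis in the documents either: there, 5 mm is an increase that confirms progression, or a default size for faint lesions.

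The objection does not rescue the label. A stated rule that attaches a causal name to any downward fluctuation mislabels tumors even in a listing.

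**Conclusion.** The concern holds as a fault of labelling and of analysis placement, and should be corrected. Under every error assumption tried, a substantial share of unchanged bystander tumors would be called abscopal: about 36% to 76% after one to four scans for a 20 mm tumor read in whole millimetres at SD 1 to 3 mm, and 24% to 50% at SD 0.5 mm. These figures rest on an assumed error SD and on errors independent between scans, with decreases judged against baseline. More scans, or comparison with the previous scan, would raise them; true growth or more ties would lower them.

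The conflict over BTR needs no assumption. It is a FEC secondary endpoint in SAP Table 2; Section 9.1 both promises its summary and sends the analysis elsewhere; Section 13 reports no change. None of this biases a planned estimate, and it does not show that a distant effect is absent.

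**What to change.** 1. Reserve the abscopal label for uninjected bystander tumors with a confirmed decrease of at least 30% in longest diameter (short axis for nodes) from the baseline before first dose. Do not use the 30% volume rule of Appendix 1 item 3. Alternatively, keep the present rule and retitle the listing *bystander tumors with any decrease*.
2. Print beside the listing the number labelled over all evaluable uninjected bystander tumors. The individual listing already holds the data.
3. Bring the FEC BTR analysis into the SAP, or into a dated addendum before database lock. Use the protocol's confirmed CR or PR over bystander tumors identified at baseline, or reconcile that with the visit-varying denominator of Appendix 1 item 4. State how a bystander tumor that is later injected is counted, because Protocol 12.2.2 also excludes tumors injected at the visit. Record the change in SAP Section 13.

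The cost is a few sentences of SAP text and a small amount of extra tabulation, with no new data. Fewer tumors will carry the label, and small tumors with large reading error will still sometimes qualify by chance.

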9.2. Progression-Free Survival and Overall Survival

Progression free survival (PFS) and Overall Survival (OS) will be evaluated for the All Treated Population, the REP, and the SEP. PFS will be defined as the time (in months) from first dose of INT230-6 to either observation of clinical deterioration, removal from study, or occurrence of death due to any cause within 126 days (approximately 2 time intervals for tumor assessments) of the last tumor assessment. Progression date will be defined as the end of treatment date as captured per eCRF guidelines when the reason for end of treatment is either 'Radiographic

deterioration' or 'Clinical deterioration.' In subjects without a progression date or with a death date more than 126 days after the last tumor assessment, the PFS time will be censored on the date of last tumor assessment or last treatment date if the subject has no post-baseline tumor assessments. PFS analyses will consider tumor assessments after treatment discontinuation.

OS will be defined as the time (in months) from first dose of INT230-6 to death. Subjects for whom death is not reported will be censored at the date of end of study.

PFS and OS will be summarized in a listing. The median time to OS as obtained from Kaplan-Meier methods will be tabulated by subgroup and will include the median, 25th percentile, 75th percentile, and a 2-sided point-wise 95% confidence interval. Hazard ratios may be determined between certain curves for the Kaplan Meier figures noted below.

A Kaplan Meier figure of OS for the All Treated, REP, and SEP populations will be presented for each of the following:

- a curve all treated monotherapy patients, a curve for subjects that received a dose to total tumor burden < 40% of tumor burden, a curve for those subjects that had a dose to total tumor burden \geq 40%,
- a curve for escalation cohort combining A1, B1, EA, EC, and a curve for escalation cohort combining EC2 and EC3,
- a curve for sarcoma patients in the monotherapy cohort and a curve for monotherapy sarcoma patients having \geq 40% of their total tumor burden treated,
- a curve for the pembrolizumab DEC/DEC2 combined cohort for subjects,
- a curve for all ipilimumab FEC cohort subjects,
- a curve for the ipilimumab FEC sarcoma subjects, a curve for all monotherapy sarcoma patients and a curve for monotherapy sarcoma subjects having \geq 40% of their total tumor burden treated will be included.

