12.1.5. Study Participation

Each subject will have their study participation documented, including the number of cycles completed, the duration of the Follow-up Period, and if discontinuing from the study, the reason for discontinuation. At the end of each cycle, the subject continuation status for each subject will be documented on the CRF.

If for any reason, either study treatment or observations were discontinued, the reason will be recorded. The primary reasons for discontinuation will be documented:

- Adverse event(s)
- Protocol violation
- Disease progression (clinical or radiological)
- Subject withdrew consent
- Subject is lost to follow-up
- Death
- Other

Subjects who discontinue from the study should be followed until resolution and/or stabilization of any adverse event. All subjects who discontinue from the study should complete Follow-up Visits to be monitored for 28 days following the last dose of INT230-6 for the occurrence of study drug-related adverse events or other clinically significant adverse event. Subjects who are unable to complete the follow-up visits should be contacted at least once within 28 days following the last dose INT230-6.

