7.6. Handling of Dropouts or Missing Data

Where individual data points are missing because of insufficient samples, dropouts, or other reasons, the data will be analyzed based on reduced denominators (e.g., using the response evaluable population). For survival analysis, dropouts without confirming events will be treated as censored.

All missing and partial start dates will be queried for a value. If a complete start date cannot be obtained, the following imputation rules apply in order to calculate duration of adverse event, concomitant medication use, or prior cancer history endpoints:

- Missing month and day
 - If the year of the incomplete start date is the same as the year of the date of study drug administration, then the missing month and day of the start date will be imputed to be the month and day of the start of study drug administration.
 - If the year of the incomplete start date is before the year of the date of study drug administration, December 31 will be assigned to the missing fields.
 - If the year of the incomplete start date is after the year of the date of study drug administration, January 1 will be assigned to the missing fields.

- Missing month only
 - If only the month is missing, the day will also be treated as missing, and both month and day will be replaced according to the above procedure.
- Missing day only
 - If the month and year of the incomplete start date are the same as the month and year of the date of study drug administration, the start date of study drug will be assigned to the missing field (i.e., AEs will be assumed treatment-emergent, and medications will be assumed concomitant).
 - If the month and year of the incomplete start date are before the month and year of the date of study drug administration, the last day of the month will be assigned to the missing field.
 - If the month and year of the incomplete start date are after the month and year of the date of study drug administration, the first day of the month will be assigned to the missing field.

If the stop date is complete and the imputed start date, when imputed as instructed above, is after the stop date, the start date will be imputed to equal the stop date.

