9. EFFICACY ANALYSES

Due to the method of action of the INT230-6 therapy observed over the course of the study, proper assessment utilizing RECIST or iRECIST was not possible. A response across all lesions using sum of diameters to assess efficacy over time using response criteria was not utilized. Thus, efficacy analyses will largely focus on the response of individual tumors (injected and bystander) as opposed to an overall tumor response, and any overall response will utilize the modified response criteria defined below.

Efficacy analyses will be conducted on the All Treated Population (ATP), the Response Evaluable Population (REP), and the Scan Evaluable Population (SEP). RECIST 1.1 assessments were not collected. Rather injected tumor response and non-injected tumor response utilizing some of the RECIST criteria were evaluated. Sponsor utilized RECIST principles with the injected and non-injected tumor measurements obtained. Efficacy will be determined based on a modified version of RECIST 1.1 criteria. Specifically, complete response (CR) and partial response (PR) will be defined for injected tumors followed per RECIST 1.1 utilizing target lesions. Progressive disease will be determined by clinical or radiological deterioration leading to the subject being taken off-treatment at the discretion of the investigator. Stable disease (SD) is defined as any adequate assessment not considered CR, PR, or progression. The appearance of a new lesion will not necessarily be considered progression and if possible will be assessed. Any post-baseline visit where a target lesion present at baseline was not assessed will result in a Not Evaluable (NE) assessment for that lesion. Data will be presented by treatment and, when indicated, by subgroups.

The primary efficacy parameter is the disease control rate (DCR), defined as the number of subjects obtaining a best overall response of either CR, PR, or SD as described above divided by the total number of subjects in the analysis population. The DCR will be presented with accompanying 95% exact binomial confidence intervals for each study part for the ATP population, REP, SEP, and by subgroup.

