5. PROGRESSION DEFINITION

Progression is defined as a patient who radiographically or clinically deteriorated as captured on any number of forms designating the patient is ending treatment or death. This includes the end of treatment form, end of maintenance form, follow-up form, and survival form. Note that typical RECIST 1.1 indications of progression such as an increase in sum of longest diameters of 20% or the presence of a new lesion are not considered progression for the purposes of PFS.

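### The PFS event list in SAP 9.2 names removal from study without a reason and omits radiographic deterioration, contradicting the plan's own progression-date and censoring rules

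*SAP*

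**What the plan says.** **SAP 9.2, event list.** PFS ends at "either observation of clinical deterioration, removal from study, or occurrence of death due to any cause within 126 days" of the last tumor assessment. The reason for removal is not specified.

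**SAP 9.2, progression date.** "Progression date will be defined as the end of treatment date as captured per eCRF guidelines", and only where the recorded reason is radiographic or clinical deterioration.

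**SAP 9.2, censoring.** "the PFS time will be censored on the date of last tumor assessment or last treatment date". This applies to anyone who has no progression date, and to anyone whose death fell outside the 126-day window. The last treatment date applies when there is no post-baseline assessment.

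**SAP 7.6.** "For survival analysis, dropouts without confirming events will be treated as censored". No censoring date is given there.

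**SAP 9.** "Progressive disease will be determined by clinical or radiological deterioration leading to the subject being taken off-treatment", at the investigator's discretion.

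**SAP Appendix 1, item 5.** "Progression is defined as a patient who radiographically or clinically deteriorated as captured on any number of forms" that record the end of treatment, or who died. Removal from study is not named.

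**Protocol 12.1.5.** The reasons for discontinuation include "Subject is lost to follow-up", withdrawn consent, adverse event, protocol violation and other. They stand beside disease progression and death as separate categories.

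**Reporting.** PFS is an exploratory endpoint in protocol 4.4 and in SAP Table 2. SAP 9.2 puts it in a listing, and the Kaplan-Meier medians and figures described there are for OS. SAP 9.1, however, says the additional endpoints, PFS among them, are summarized by treatment and subgroup. Protocol 14.3.3 has PFS summarized in the same way as its Kaplan-Meier endpoints.

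**The concern.** A time-to-event endpoint needs one rule that gives each subject a status and a time. Here the event list and the rules that follow it give different answers for a subject who leaves the study alive and without deterioration. A programmer who codes the event list literally records an event at removal. One who codes the progression-date and censoring rules records a censored time.

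The event list also leaves out radiographic deterioration, which the next sentence and Appendix 1 item 5 both include. So the list is too wide in one respect and too narrow in another, which suggests that it, and not the censoring rule, is the faulty part.

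At stake is whether a reported PFS status reflects disease or only departure from the study.

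**Working it through.** **1. The one number in the rule.** Tumor imaging recurs every 9 weeks after the 12-week scan (SAP 4.4). Two intervals are 2 × 9 × 7 = 126 days, so the 126-day window reproduces exactly. It is not in dispute.

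**2. The rules side by side.** Take three subjects and apply each rule:

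| Subject | 9.2 event list | 9.2 date and censoring rules | 7.6 | Appendix 1 item 5 |
|---|---|---|---|---|
| Withdraws consent or is lost, alive, no deterioration | Event | Censored | Censored | Not progression |
| Treatment ended for radiographic deterioration | Not named, unless read as a removal | Event | Not applicable | Progression |
| Treatment ended for clinical deterioration | Event | Event | Not applicable | Progression |

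The event list stands alone in the first row and is incomplete in the second.

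**3. Who can change status.** Only a subject whose first exit is a removal, with no earlier progression and no death within 126 days of the last tumor assessment. A subject who progressed and was lost later already has an event. So does one who left and has a recorded death inside the window.

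**4. The time changes too.** Suppose a subject has the 12-week scan (84 days) and is removed when the next scan is due, without having it (84 + 63 = 147 days). Under the event list this is an event at 147 days. Under the censoring rule it is a censored time of 84 days. SAP 8.1 lists study discontinuation with its own date and reason, apart from discontinuation of study drug, so the data for a literal coding would be available.

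**5. Possible size (illustration).** The documents give no count of such removals. Let w be the share of first exits that are removals without deterioration or qualifying death. Assume constant, independent hazards, a median of 3.0 months when removals are censored, and the same exit time under both codings.

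- Progression or death hazard: λ = ln 2 / 3.0.
- Removal hazard: λw / (1 − w).
- Total hazard if removals are events: λ + λw / (1 − w) = λ / (1 − w).
- Median if removals are events: 3.0 × (1 − w).

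| w (assumed) | Subjects switching, 110 × w | Median by formula (months) | Simulated median, censored | Simulated median, event |
|---|---|---|---|---|
| 10% | 11 | 2.7 | 3.01 | 2.75 |
| 20% | 22 | 2.4 | 3.02 | 2.44 |
| 30% | 33 | 2.1 | 3.03 | 2.13 |

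The simulation used 500 runs of 110 subjects, the final enrollment in SAP 5. The counts assume that all 110 have an observed first exit. Under this model, counting removals as events shortens PFS.

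**The case against.** The strongest reply is that the operating rules already settle the matter. The progression-date rule, the censoring rule, SAP 7.6 and Appendix 1 item 5 all point to censoring a withdrawal, against one loose phrase. Appendix 1 holds the programming instructions, and item 5 is written expressly for PFS. On this view the phrase is shorthand for being taken off treatment for radiological deterioration, the limb missing from the event list; SAP 9 defines progressive disease in similar terms. Neither document defines removal from study, so it is an inference that it covers every withdrawal and loss.

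Much of this stands. A reader might infer that the SAP turns withdrawals and losses into progressions. The documents do not support that, because the other rules would censor those subjects. Nor do they show that PFS cannot be reproduced, or that every removed subject would switch status.

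What does not fall away is the contradiction. The shorthand reading has to be supplied by the reader. SAP 8.1 treats leaving the study and stopping study drug as different facts with different dates, which makes a literal coding possible. A listing also needs a status and a time for each subject.

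The reply is also right that PFS is exploratory in a non-randomized study and that no primary or secondary endpoint uses it.

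**Conclusion.** The point holds as an internal contradiction. The event list in SAP 9.2 does not agree with the progression-date and censoring rules in its own paragraph, with SAP 7.6, or with Appendix 1 item 5. A subject removed alive without deterioration can be coded either way.

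The number affected cannot be taken from the documents. The illustrated fall from 3.0 to between 2.7 and 2.1 months rests on an assumed 10% to 30% of first exits, an assumed median, and constant independent hazards. It shows that a PFS estimate could move materially, not that this one did.

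The practical weight is modest: PFS is exploratory and 9.2 reports it in a listing. It is not nil, because SAP 9.1 and protocol 14.3.3 leave room for a summary.

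**What to change.** In SAP 9.2:

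- Delete removal from study from the event list.
- Define the event as radiographic deterioration, clinical deterioration, or death from any cause within 126 days of the last tumor assessment.
- State that all other removals are censored under the existing 9.2 rule: at the last tumor assessment, or at the last treatment date if there is no post-baseline assessment. This agrees with 7.6, which supplies the principle but not the date.

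In Appendix 1 item 5, use the same wording. In particular, add the 126-day limit, since the item now counts death without one.

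The cost is a few sentences of SAP text and a check that the PFS program follows them. No new data are needed. SAP section 2 requires the plan and any deviations from it to be final before database lock, so the edit belongs before that point.
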